4.1.3 Donor PBPC

- h) Donors will receive G-CSF injections daily from day -5 to day 0. G-CSF will be administered

subcutaneously at a dose of 16 µg/kg/day. Collection of peripheral blood progenitor cells (PBPC's) will be performed by apheresis. Collections generally occur on day -1 and day 0 if needed. CD34⁺ proportion will be evaluated by flow cytometry. Patients will receive all cells collected. The ideal cell doses (based on recipient body weight) for MRD and MUD transplants are > 5x10⁶ CD34⁺ cells/kg. Cells collected on days -1 and 0 will be processed for infusion on day 0. Fresh cells (not frozen) are to be infused whenever possible. Patients will receive premedication approximately 1 hour prior to infusion using current standard of care or as recommended:

- i) Acetaminophen: 650 mg p.o., Diphenhydramine: 50 mg i.v., Hydrocortisone: 100 mg i.v., 1 hour prior to infusion.
- j) For MRD transplants, if the target cell dose is not achieved then a third apheresis procedure may be performed on day +1 and the cells infused on the same day. If after a third apheresis procedure the CD34 dose is <3x10⁶/kg and the total CD3 cell dose does not exceed 5x10⁸/CD3⁺ cells per kg, then a fourth apheresis procedure may be performed on day +2 and the cells infused on the same day. Total CD3⁺ cell dose should not exceed 7x10⁸ CD3⁺ cells/kg. Grafts that contain >7x10⁸ CD3⁺ cells/kg must first be evaluated by the Principal Investigator before infusion. Administration and premedication prior to cell infusion will be identical to those specified for day 0.
- k) Collection of cells for the MUD transplants will be coordinated through the National Marrow Donor Program and subject to the rules of that Program, thus MUD collections will be limited to days -1 and 0 only. If mobilized PBPC is not available through certain NMDP collection centers then bone marrow will be considered.
- l) ABO incompatibility: ABO incompatibility between donor and host will require red cell depletion only if bone marrow is used as the hematopoietic source. Red cell depletion is performed by Hetastarch sedimentation according to standard procedure.
- m) Post-Transplant Growth Factors: Patients should not receive post-transplant growth factors while receiving MMF, particularly during the first month off MMF taper. Growth factors should not be given unless severe neutropenia develops or persists past day 27 post-transplant (ANC < 100/ml for > five days).

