4.1.4 Immunosuppression for GVHD prophylaxis

- n) Immunosuppression will include tacrolimus (Prograf) and mycophenolate mofetil (MMF). Tacrolimus will be administered orally at a dose of 0.03 mg/kg/day bid from day -3 through day +56. MMF will begin at 15 mg/kg p.o. bid for MRD and Q 8 hours for MUD from the evening of day 0 to day +27 for MRD or day + 40 with a taper for MUD. Prograf dose adjustments will be made as clinically indicated. Trough levels will be monitored to keep the Tacrolimus level in the range of 8-10 ng/ml. MMF dose adjustments will be made if there is evidence of MMF-related GI toxicity or myelosuppression.
- o) Tacrolimus (Prograf): Tacrolimus is given at 0.03 mg/kg p.o. b.i.d (9 am and 9 pm) from day -3 until after the day +56 chimerism studies have been obtained. Doses should be adjusted to maintain a high therapeutic Tacrolimus level to between 8-10 ng/ml, unless there is renal insufficiency (creatinine >2.0) or hyperbilirubinemia (bilirubin >2.0) in which case the Tacrolimus should be reduced to normalize these parameters. If there is nausea and vomiting at any time during FK506 treatment, Tacrolimus should be administered intravenously by continuous infusion at 3 mg/kg over 20 hours, and adjusted for the Tacrolimus blood level. Tacrolimus will be tapered per standard guideline of Stanford BMT program after the day +56 chimerism studies are obtained. If patient does not tolerate Tacrolimus, tacrolimus may be used and administered per standard guideline of Stanford BMT program.
- p) Mycophenylate mofetil (MMF): Administration of MMF will begin at 15 mg/kg po on day 0, at 5-10 hours after mobilized PBPC infusion is complete. Thereafter, beginning on day +1 MMF is taken at 15 mg/kg po b.i.d. (30 mg/kg/day) if transplantation was using a matched related donor, and 15 mg/kg po Q8 hours if from a matched unrelated donor or a one antigen mismatched donor. Doses will be rounded up to the nearest 250 mg (capsules are 250 mg). MMF will be stopped on day +28 for matched related donors and for one antigen mismatched or unrelated donors beginning day +40. MMF will be tapered by 10% weekly till off, typically by day +96. If there is nausea and vomiting at any time preventing the oral administration of MMF, MMF should be administered intravenously.

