- q) Guidelines for MMF dose adjustment: If in the clinical judgment of the investigator, there is documented toxicity related to MMF administration, a dose adjustment will occur. Based on previous solid organ transplantation studies, dose adjustments are likely to occur because of hematopoietic or gastrointestinal adverse effects. Dose adjustments will not be made for hematopoietic toxicities unless severe neutropenia develops or persists until day +21 post-transplantation (ANC <100/ml for >5 days). In the event of gastrointestinal toxicity that requires medical intervention including

medication for control of persistent vomiting or diarrhea that is considered to be due to MMF, a 20% dose reduction or the drug will be given i.v. For severe gastrointestinal toxicity related to MMF (severe refractory diarrhea or overt gastrointestinal bleeding), MMF may be temporarily stopped.

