4.2 General Concomitant Medication and Supportive Care Guidelines

- 4.2.1 Supportive care measures will be consistent with standard practice of the Stanford BMT Program. Standard care measures are included by not limited to measures for skin care, mucositis, nausea, diarrhea, constipation, pain control, infection prevention and patient and family education.
- 4.2.2 Transfusion support for red blood cells and platelets will be consistent with standard practice of the Stanford BMT Program.

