PR	(1) Cumulative reduction $\geq 50\%$ of the SPD sum of the maximum linear dimension (major axis) x longest perpendicular dimension (minor axis) of each abnormal lymph node at baseline and no new lymph node ≥ 1.5 cm or >1.0 cm in the short axis if long axis 1-1.5cm diameter.
SD	Fails to attain the criteria for CR, PR and PD
PD ♦	(1) $>50\%$ increase in SPD from baseline of lymph nodes or (2) Any new node ≥ 1.5 cm in greatest transverse diameter or >1 cm in short axis diameter if 1-1.5 cm in long axis that is proven to be N ₃ histologically or (3) Loss of response: in those with PR or CR, $>50\%$ increase from nadir in SPD of lymph nodes
Relapse	Any new lymph node ≥ 1.5 cm in long axis diameter in those with CR

* Peripheral and central lymph nodes.

♦ Whichever criterion occurs first.

Response in Blood*

CR**	B_0
PR [#]	>50% decrease in quantitative measurements of blood tumor burden from baseline in those with high tumor burden at baseline (B_2)
SD	Fails to attain criteria for CR, PR or PD
PD [*]	(1) B_0 to B_2 or (2) >50% increase from baseline and at least 5,000 neoplastic cells/ μ L ⁴² or (3) Loss of response: 1. in those with CR who were B_1 or B_2 at baseline, increase in neoplastic >1000 neoplastic cells/ μ L or 2. in those with PR who were originally B_2 at baseline, >50% increase from nadir and at least 5,000 neoplastic cells/ μ L
Relapse	Increase of neoplastic blood lymphocytes to $\geq B_1$ in those with CR

* As determined by absolute numbers of neoplastic cells/uL.

** If a bone marrow biopsy was performed at baseline and determined to unequivocally be indicative of lymphomatous involvement, then to confirm a global CR where blood assessment now meets criteria for B_0 , a repeat bone marrow biopsy must show no residual disease or the response should be considered a PR only.

There is no PR in those with B_1 disease at baseline as the difference within the range of neoplastic cells that define B_1 is not considered significant and should not affect determination of global objective response.

* Whichever occurs first.

Response in Viscera

CR	Liver or spleen or any organ considered involved at baseline should not be enlarged on physical exam and should be considered normal by imaging. No nodules should be present on imaging of liver or spleen. Any post treatment mass must be determined to be biopsy to be negative for lymphoma.

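### The severe-neutropenia trigger for MMF adjustment and growth factors is printed as ANC <100/ml, almost certainly a 1,000-fold unit slip for µL

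*Combined protocol and SAP*

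**What the plan says.** Two treatment rules in section 4 of the combined protocol and SAP depend on an absolute neutrophil count (ANC).

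- **Section 4.1.4, item q (MMF):** "Dose adjustments will not be made for hematopoietic toxicities unless severe neutropenia develops or persists until day +21 post-transplantation (ANC <100/ml for >5 days").
- **Section 4.1.3, item m (growth factors):** "Growth factors should not be given unless severe neutropenia develops or persists past day 27 post-transplant (ANC < 100/ml for > five days").

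The day differs between the two, but the count, the unit and the duration are the same. These are the only ANC thresholds in the documents.

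Four other places bear on how the rules would be applied:

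- Item q opens with a general provision: "If in the clinical judgment of the investigator, there is documented toxicity related to MMF administration, a dose adjustment will occur".
- Section 4.1.4, item n, gives no cut-off: "MMF dose adjustments will be made if there is evidence of MMF-related GI toxicity or myelosuppression".
- Section 4.2 refers to local practice: "Supportive care measures will be consistent with standard practice of the Stanford BMT Program".
- Appendix C, in the footnote to the blood response table, states its unit for circulating tumour cells: "As determined by absolute numbers of neoplastic cells/uL".

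**The concern.** A limit of 100 neutrophils per millilitre is not a workable definition of severe neutropenia. It is a tenth of a cell per microlitre, so a patient with even one neutrophil per microlitre would fall outside the rule.

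Both items are operative instructions. Item q is worded as a prohibition with one exception, and the printed unit makes that exception practically unreachable. It also sets item q against item n, which calls for MMF adjustment when there is myelosuppression. Item m discourages growth factors on the same terms.

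The patients are prone to infection. Section 2.1 notes that compromised skin raises the risk, and section 4.1.5 expects susceptibility to opportunistic infection for at least 6 months. Under section 4.1.4, item p, recipients of unrelated or one-antigen-mismatched grafts typically stay on MMF until about day +96, so the rule can be in force for months. If staff silently substitute another unit, adherence cannot be judged against the written text.

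**Working it through.** The plan derives no figure here, so there is nothing to reproduce. The check is a unit conversion followed by a search for any text that corrects it.

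**Inputs**

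- Printed limit: 100/ml (section 4.1.3, item m; section 4.1.4, item q).
- Conversion: 1 ml = 1,000 µL; 1 L = 1,000 ml.
- Intended limit: 100/µL. This is an assumption, because the documents do not state it.
- Laboratory reporting resolution: not given. A range of 1, 10 or 100 cells/µL is assumed.

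**Printed limit**

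- Per microlitre: 100 ÷ 1,000 = 0.1 cell/µL.
- Per litre: 100 x 1,000 = 100,000/L = 0.0001 x10^9/L.

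**Assumed intended limit**

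- Per millilitre: 100 x 1,000 = 100,000/ml.
- Per litre: 100,000 x 1,000 = 100,000,000/L = 0.1 x10^9/L.

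**Ratio:** 100,000/ml ÷ 100/ml = 1,000.

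**Smallest non-zero count the laboratory could report, against the printed limit**

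| Assumed resolution | In cells/ml | Multiple of 100/ml |
|---|---|---|
| 1/µL | 1,000 | 10 |
| 10/µL | 10,000 | 100 |
| 100/µL | 100,000 | 1,000 |

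At each resolution the smallest reportable non-zero count lies above the limit, so only a reported zero satisfies the trigger.

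**Is it corrected elsewhere?** No.

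- Section 4.1.4, item n, mentions myelosuppression without a value.
- Section 6 says only that doses are not modified.
- The abbreviation list does not define ANC.
- The record of changes includes edits to section 4.1.4, but none to this unit.
- The blood criteria in Appendix C use cells per microlitre, with limits of 1,000 and 5,000. They concern tumour cells, so they show a convention in the document and not the unit meant for ANC.

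**Could the unit be a text-conversion fault?** This is unlikely. The same unit appears in two separately worded items, and the micro sign survives in section 4.1.3, item h, where the G-CSF dose is given in µg/kg/day. Only the source page can exclude it.

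**The case against.** The strongest reply is that the slip is too obvious to mislead. A transplant physician would see that 0.1 cell/µL is impossible as a working limit and would read µL. The surrounding text also leaves room: item q is headed as guidance and starts from the investigator's judgment, item n allows adjustment for myelosuppression, item m is advisory, and supportive care follows program practice. Section 2.2 reports minimal neutropenia in the first 37 patients given this conditioning, so few may come near either trigger. All of this stands as a reason to expect a small practical effect, although that series was in other hematological malignancies and is only indirect support. It does not make the printed limit right.

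A second reply concerns the wording. Both items speak of neutropenia that develops or persists, and the bracketed count could be attached to persistence alone, leaving onset to clinical judgment. That reading is possible but strained. The bracket most naturally defines severe neutropenia for both branches.

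A third reply is that neither the intended unit nor a faithful text conversion is proven. That is correct. Both are inferences, which is why the remedy begins with the source page and the investigator's confirmation.

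**Conclusion.** The concern holds. Items m and q print a severe-neutropenia limit equal to 0.1 cell/µL, and nothing in the documents corrects it. If 100/µL was meant, the printed limit is 1,000-fold too low.

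The conversion is certain. The intended unit is an inference from the unworkability of the printed value, supported by the per-microlitre counts in Appendix C. The finding that only a reported zero qualifies depends on the assumed laboratory resolution, but it is the same across the range of 1 to 100 cells/µL. The documents give no basis for counting affected patients, so none is projected.

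The point should be fixed because it is the decision threshold in two safety-relevant treatment rules. It has no bearing on the sample size, the safety stopping boundaries or the analysis of 180-day PFS.

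**What to change.** 1. Check the source page for both items. If it already reads µL, no amendment is needed.
2. Otherwise, change the unit in section 4.1.3, item m, and section 4.1.4, item q, to ANC <100/µL (0.1 x10^9/L), once the investigator has confirmed that this is the intended threshold.

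The cost is a unit correction in two items. No procedures, visits or patients are added.

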4.1.5 Infection Prophylaxis

- r) It is expected that patients on this protocol will be susceptible to opportunistic infections in the post-transplant period for at least 6 months. These expectations are based upon prior experiences with patients that have undergone treatment with TLI and/or ATG, as well as other non-myeloablative allogeneic transplantation procedures. Infectious disease prophylaxis will be according to the current standards of care of Stanford BMT program.

4.1.6 Engraftment and Disease Status Monitoring

- s) Patients will be followed in the ITA for signs of infection or GVHD. Monitoring for engraftment and infection will be according to current standard of care of Stanford BMT program.
- t) Chimerism: Microsatellite analysis (VNTR) of CD3, CD19, CD15, and CD56 peripheral blood cell subsets will be performed on days +28 (\pm 5 days), +56 (\pm 5 days), +90 (\pm 14 days), +180 (\pm 14 days), +270 (\pm 14 days), and yearly (\pm 4 weeks) to evaluate the degree of donor hematopoietic cell engraftment (donor chimerism), and on bone marrow on day +90 (\pm 14 days), and yearly per physician's discretion.
- u) Clinical response will be determined at 3, 6, 9, 12, 18, 24 months or until relapse or progression after transplant. The disease status and clinical response will be scored on a rigorous and multifactorial approach described before (41, appendix). This approach takes tumor burden in skin, lymph nodes and blood into consideration. To achieve this, patients will be evaluated at Cutaneous Lymphoma Clinic before transplant and at specified time points after transplant.

4.1.7 Therapeutic Interventions for Disease Progression

- v) Early discontinuation of immunosuppression (< day +120) should be considered the first therapeutic maneuver. However, neither MMF nor Tacrolimus should be stopped prior to reviewing chimerism results. If the donor T cell chimerism in blood is \geq 50% and there is < grade II GVHD, MMF is to be stopped if still being taken, and Tacrolimus tapered over two weeks. Bone marrow aspirate and blood chimerism studies will be performed two weeks after discontinuation of immunosuppression.
- w) For Sezary Syndrome patients, lymphoma cells in the blood (Sezary cells) will be monitored by flow cytometry on days +28, and then 3, 6, 9, 12, 18, 24 months after transplant as described for clinical response determination. Patients with persistent Sezary cells on day +28 will have the option to start extracorporeal photopheresis (ECP) on day +30 \pm 5. The recommendation is to administrate four weekly treatments at the discretion of the investigator, followed by additional four monthly treatments, and to be re-evaluated.

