1. OBJECTIVES

1.1 Primary Objectives

To evaluate the graft versus lymphoma effect by monitoring rate of clinical response, event-free and overall survival.

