For patients with refractory disease to skin-directed therapies or with advanced stage of MF (IIB-IV) and Sezary syndrome, systemic treatments should be included in the primary therapy strategy, with or without skin-directed treatments. The first category of systemic therapy is mild immunomodulating agents (biologics), such as systemic retinoids (bexarotene) (7), interferons (8,9), low dose methotrexate and newer reagents, histone deacetylase inhibitors (10), and denileukin diftitox (11). While these treatments have a slow time to response and generally provide partial response rates no greater than 50%, their lack of cumulative toxicity allows them to be used as maintenance treatment for long periods. Extracorporeal photopheresis (ECP) has been used as monotherapy or in combination with other systemic therapy and has been shown to be a very effective treatment, especially for disease control of SS (12). The next category of systemic therapy is more traditional cytotoxic chemotherapy. The most common reagents are liposomal doxorubicin, gemcitabine, chlorambucil and high dose methotrexate. Pegylated liposomal doxorubicin is effective as a single agent. In a prospective study, every 4 week infusions gave an overall response rate of 84% with 42% of the patients achieving complete response (13). However, these responses are usually short-lived and patients move from one agent to another agent, then proceed to combination chemotherapies, and eventually progress after multiple therapies.

Treatment with Hematopoietic Stem Cell Transplantation

Emerging data on allogeneic HSCT, particularly using non-myeloablative conditioning, suggest the existence of a graft-versus-T cell lymphoma effect. Allogeneic transplant should be considered in patients with advanced disease who fail to respond to all primary therapies or do not have durable response with salvage treatments.

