2.3 Rationale

Mycosis Fungoides (MF) and its leukemic variant, Sezary Syndrome (SS) is the most common type of cutaneous non-Hodgkin's lymphoma (NHL) in North America. Though most of the patients have an indolent course with median survival of 12-15 years, those with advanced diseases have a survival of 1-3 years after diagnosis, and there is no curative therapy (1). While localized skin treatment, novel biological therapies such as histone deacetylase inhibitors, or systemic chemotherapy can temperately control the diseases, none of these provide a long-term remission. Graft-versus-lymphoma effects after allogeneic hematopoietic stem cell transplantation (HSCT) have been demonstrated to provide a long-term disease control in B cell lymphoma, including low-grade B cell lymphoma and chronic lymphocytic leukemia. We propose a clinical trial using non-myeloablative allogeneic HSCT to treat patients with advanced stage MF/SS. The rationale is that graft-versus-lymphoma provided by this non-myeloablative approach will result in a clinical response and a prolonged progression free survival in these patients. The patient population enrolled in this clinical trial will be those with MF/SS who still have persistent or progressive disease after being treated with multiple lines of local and systemic therapies. When MF/SS reached this stage of their disease, the conventional chemotherapies will no longer provide any clinical benefit. Therefore, we proposed using this low toxicity allogeneic HSCT protocol to these patients.

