12.1 Endpoints

12.1.1 Primary endpoint

The primary efficacy endpoint is PFS at 180 days (defined above). The safety endpoints include GVHD and other treatment related events, including mortality.

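### Post-transplant ECP in some Sezary syndrome patients falls inside the 180-day PFS window, and no efficacy analysis separates its contribution from the graft-versus-lymphoma effect

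*Combined protocol and SAP*

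**What the plan says.** The primary objective in section 1.1 is "To evaluate the graft versus lymphoma effect by monitoring rate of clinical response, event-free and overall survival". Section 2.3 makes the same attribution: "The rationale is that graft-versus-lymphoma provided by this non-myeloablative approach will result in a clinical response and a prolonged progression free survival in these patients". Section 12.1.1 then fixes the endpoint: "The primary efficacy endpoint is PFS at 180 days".

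Section 4.1.7 adds a treatment after transplant for one group. "For Sezary Syndrome patients, lymphoma cells in the blood (Sezary cells) will be monitored by flow cytometry on days +28" and at later visits; then "Patients with persistent Sezary cells on day +28 will have the option to start extracorporeal photopheresis (ECP) on day +30", with a window of plus or minus 5 days. On the course it says: "The recommendation is to administrate four weekly treatments at the discretion of the investigator, followed by additional four monthly treatments, and to be re-evaluated". Section 2.1 says that ECP "has been shown to be a very effective treatment, especially for disease control of SS", and section 4.1.2(g) notes its US approval for cutaneous T cell lymphoma.

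The efficacy sections do not mention ECP. Event-free survival in 10.1.6 ends at recurrence or death. PFS in 12.3.2 is the probability of being alive without progression. The subsets in 12.2 are transplanted patients and engrafted patients. Section 12.3.3 treats non-adherence as failure to complete preparation and transplant. Section 12.3.6 relates outcomes to chimerism and other markers, as exploration. The ECP-specific items are laboratory ones: regulatory T cell monitoring (2.4.4) and samples before and after ECP (Correlative Study Calendar, section 9).

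**The concern.** By the protocol's own account ECP acts against the disease under study. It is offered because lymphoma cells are still present, and it can run through most of the period on which the primary endpoint is judged. Sections 1.1 and 2.3 nevertheless treat response and freedom from progression as evidence of what the graft does. This is a single-arm study, so only the analysis can show how much of a good result came with ECP and how much without. If the plan is followed as written, a response or an event-free status reached during ECP is counted towards the graft effect with nothing in the report to show it. What is at stake is the interpretation of the stated objective in the ECP-treated SS patients, not the validity of the PFS estimate itself.

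**Working it through.** **Step 1. The plan's own precision figure.** Section 12.4.2 gives 58% to 88%, half-width 15%, for 27/36. The exact (Clopper-Pearson) interval for x successes in n has lower limit Beta⁻¹(0.025; x, n−x+1) and upper limit Beta⁻¹(0.975; x+1, n−x). For 27/36 it is 57.8% to 87.9%, half-width 15.0%. The widest half-width at n = 36 is 17.1%, at 18/36. Both agree with the plan, so the exact interval is used below. (The Wald interval, 60.9% to 89.1%, does not match.)

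**Step 2. When ECP is given.** Inputs from 4.1.7: start day s between 25 and 35, four weekly treatments, then four monthly ones. Assumptions: a month is m = 28 or 30 days, and the first monthly treatment comes one month after the last weekly one.

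- Weekly treatments: days s, s+7, s+14, s+21.
- Last monthly treatment: day s + 21 + 4m.
- Earliest end: 25 + 21 + 112 = day 158. Latest end: 35 + 21 + 120 = day 176.
- Length of course: 21 + 4m = 133 to 141 days, or 133/180 = 74% to 141/180 = 78% of the window.
- The fifth treatment falls no later than 35 + 21 + 30 = day 86, and the sixth no earlier than 25 + 21 + 56 = day 102. So five of eight treatments precede day 90.

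Sections 4.1.6(u) and 10.1.1 put the first post-transplant response determination at 3 months. No response time point set there therefore precedes ECP. The correlative calendar lists a dermatology assessment at day +30, but that is not one of the response time points.

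**Step 3. Whether ECP can change a scored outcome.** In Appendix C, progression in blood needs a move from B0 to B2, or a rise of more than 50% from baseline to at least 5,000 cells/µL, or loss of a response. Persistent cells alone do not meet this, so a patient can start ECP and remain event-free at day 180. Global CR needs every category to be in CR or not involved. With a skin PR and another category involved at baseline, global PR needs CR or PR in at least one such category; otherwise the score is SD. Clearing the blood during ECP can therefore move SD to PR, or PR to CR.

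**Step 4. Size, as an illustration.** The number of SS patients and of ECP users is not given. Let k be the number of patients event-free at day 180 who had started ECP. If each were counted as a failure, the plan's example becomes (27 − k)/36. With the minimum follow-up of 1 year promised in 12.4.2 and no one lost before day 180, Kaplan-Meier at day 180 equals this proportion.

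| k (assumed) | Event-free without ECP | Rate | Exact 95% CI |
|---|---|---|---|
| 0 | 27/36 | 75% | 58% to 88% |
| 2 | 25/36 | 69% | 52% to 84% |
| 3 | 24/36 | 67% | 49% to 81% |
| 4 | 23/36 | 64% | 46% to 79% |
| 6 | 21/36 | 58% | 41% to 75% |

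At the maximum of 40 patients, 30/40 = 75% (59% to 87%) becomes 26/40 = 65% (48% to 79%) for k = 4. These are lower bounds under an assumed k, not estimates of what ECP contributes.

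**The case against.** The strongest reply is that ECP belongs to the treatment plan: it is described in 4.1.2(g), scheduled in 4.1.7 and has its risks listed in 7.1. Section 12 states its goal as proof of concept for transplant with TLI/ATG, and nowhere says that PFS isolates the graft. PFS regardless of ECP serves that goal. This stands, and a reader who infers that the primary analysis is wrong goes further than the documents allow.

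A second reply is that counting ECP start as failure does not measure the graft effect either. The trigger is persistence at day +28, not progression. Section 2.2 suggests that the graft effect may be slow, and tacrolimus runs to day +56. A slow graft responder may still have Sezary cells at day +28, and because ECP is optional the figure also reflects uptake. This stands too: the figure is a pessimistic bound.

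Third, attribution is uncertain elsewhere as well. Total skin electron beam therapy is given for cytoreduction before transplant, and section 2.4.4 reports that ECP may itself act through regulatory T cells. The planned chimerism analyses also bear on attribution. So it would be too strong to say that the trial cannot support its hypothesis at all in these patients. But none of this shows the reader how outcomes divide by ECP use, and that gap remains.

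**Conclusion.** The point holds within limits. It concerns only SS patients with persistent Sezary cells on day +28 who choose ECP. For a full recommended course, treatment ends at about day 158 to 176 and covers about three quarters of the 180-day window; a shorter course covers less. In these patients response, event-free survival and PFS reflect transplant plus ECP, and the plan has no efficacy analysis that makes this visible.

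The size is unknown. The example of three patients, 75% falling to a lower bound of 67%, rests on an assumed count and on treating every ECP start as a failure. A reader might infer that the true PFS is 67% or less, or that a lower limit under 50% means the result is not encouraging by the plan's own standard. Neither follows. The remark about 50% in 12.4.2 concerns the PFS result itself, not a confidence limit and not a composite that counts ECP start as failure. This is an inexpensive improvement that decides what the trial can say about its own objective.

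**What to change.** Keep primary PFS unchanged, and state in 12.1.1 that it applies to the transplant strategy regardless of ECP. Require ECP start dates to be recorded; the calendars list samples before and after ECP, but the documents do not say that the dates are trial data. Then add to 12.3.2:

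- **(a) A descriptive report** of response and 180-day PFS by disease (MF or SS) and by ECP use, with the number of responses reached before or without ECP. On the present response schedule this will mostly be responses without ECP.
- **(b) A supporting sensitivity analysis** in which starting ECP or another new anti-lymphoma therapy before day 180 counts as a PFS failure and as non-response. Withdrawal of immunosuppression should not count, since it works through the graft. Label the result as a pessimistic lower bound, not as an estimate of the graft effect. Do not censor at ECP start instead: ECP is given for persistent disease, so that censoring would probably be informative.

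State that results in ECP-treated patients reflect transplant plus ECP. The sensitivity analysis should inform the discussion and not act as a formal gate on the conclusion.

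The cost is a short addition to the analysis section, a little more data recording and a less favourable supporting figure. No change to clinical management is proposed.
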